- Patients with inability to take medication orally due to swallowing problems in which it is not indicated to place a nasogastric tube.
- Pregnant or breastfeeding patients.
- Patients in a GCS 3 points situation with bilateral dilated pupils.
- Patients with associated spinal cord injuries.
- Patient with any systemic condition that contraindicates the use of corticosteroids.

Randomization

To ensure a balanced sample size across groups over time, the statistician of the study will apply the block randomisation method with a block size of 2 (two possible sequences: AB and BA) and will be generated with the statistical package R, version 3.5.3, a list for each hospital. A limited number of treatments will be available in each

hospital, sent from the Pharmacy Department of Son Espases Hospital, which will be numbered, and will be assigned in a correlative manner.

Patients, clinical staff, evaluators of the results as well as the statistical team will be blinded to the assignment of medications.

Only the pharmacist, who masks the capsules and labels the containers, will know the assignment of the codes, and will keep them blind until the last phase of the study, after the main statistical analysis, or when unmasking is required.

Once it is verified that the patient meets all the inclusion criteria and none of the exclusion criteria, and after signing the informed consent by the patient himself or by the closest relative, the doctor responsible for the patient will correlative assign the number to the patient.

Settings

Initially, the study will be carried out in Son Espases Hospital (Palma de Mallorca) and 12 de Octubre Hospital (Madrid). During the first year, all possible patients will be tried to be recruited. A minimum of 60 patients are expected between the two hospitals.

If after the first year interim analysis the Trial Steering Committee (TSC) decides to continue the trial, recruitment will begin in the hospitals included in the Spanish National Registry of Traumatic patients in the ICU (RETRAUCI Network) which includes 56 public hospitals.

Outcome measures

After a patient has been randomized, the outcome will be collected even if the trial treatment is interrupted or is not actually given

Primary outcome

The primary outcome is the functional status (outcome) of TBI patients one and six months after the trauma according to the Glasgow Scale Outcome Extended (GOSE).

Secondary outcomes (Supplemental data)

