Dexamethasone doses are those commonly used in neurooncology and there is an extensive experience in its use. It will be a short and descending course: 4mg/6 hours (2 days); 4 mg/8 hours (2 days); 2 mg/6 hours (2 days); 2 mg/8 hours (2 days); 1 mg/8 hours (2 days); 1 mg/12 hours (2 days).

Drug manufacture, blinding and supply of trial treatment

Dexamethasone (Forteocortin®) will be acquired from ERN, SA. Laboratories (Barcelona, Spain). The Son Espases Pharmacy Department will be in charge of developing and conditioning the 4mg, 2mg and 1mg dexamethasone / placebo capsules needed for 12 days of treatment, keeping the researchers blind.

The preparation and conditioning of the capsules will be carried out following the standardized work procedures of the pharmaceutical laboratory and its quality controls, previously authorized by the Agencia Española del Medicamento (AEMPS).

The Son Espases Pharmacy Department will be responsible for identifying the containers and sending them by courier to the participating hospitals. A record of the dispensing of test samples will be kept and will be sent in acknowledgment of receipt for control.

Patients, clinical staff, evaluators of the results as well as the statistical team that will perform the analysis will not know the assigned treatment. A randomization list will be created for each hospital. The randomization sequence will only be known by the Pharmacy Department of Son Espases Hospital.

Administration of trial treatment

Each patient will receive 3 containers with the correspondingly identified doses, and an information sheet explaining dose and frequency for proper oral administration.

Other treatments for traumatic brain injury

There is a wide spectrum of treatments for TBI. As the trial will be conducted in Spain, each participating site should follow its own clinical guidelines for the treatment of TBI patients. There is no need to withhold any clinically indicated treatment in this trial.

Dexamethasone or placebo would be provided as an additional treatment to the usual management of TBI.

Safety and Adverse events

Dexamethasone has a well documented safety profile. Nevertheless, data on adverse events, such as infectious complications, hyperglycemia, gastro intestinal bleeding or appearance of psychotic symptoms will be collected as secondary outcomes and will be presented to the independent Data Monitoring Committee (DMC) for blinded review.

Definitions

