Adverse events (AE): Any undesirable and unintended medical occurrence affecting a trial participant during the course of a clinical trial.

Serious adverse events (SAE): A serious adverse event (experience) is any undesirable medical occurrence that results in death or is life-threatening or requires inpatient hospitalization or prolongation of existing hospitalization, or results in persistent or significant disability/incapacity.

Reporting of adverse events for this trial

Death, life-threatening complications, and prolonged hospital stay which is attributable to the adverse event are pre-specified outcomes to be reported in this trial. This clinical trial is being conducted in an emergency condition using a drug in common use. It is important to consider the natural history of the critical medical event affecting each patient enrolled, the expected complications of this event, and the relevance of the complications to dexamethasone.

Adverse events to be reported using an adverse event reporting form will be limited to those trial outcomes that might occur and be reasonably attributable to the trial drug. Events that are part of the natural history of the primary event of TBI or expected complications of TBI should not be reported as adverse events.

If an SAE occurs, a written report must be submitted within 24 h. The Trial Steering Committee (TSC) will coordinate the reporting of all SAEs to all relevant Regulatory Agencies, Ethics Committees and local investigators as per local legal requirements.

Unblinding

In general there should be no need to unblind the allocated treatment. Unblinding should be done only in those rare cases when the clinician believes that clinical management depends importantly upon knowledge of whether the patient received dexamethasone or placebo. In those few cases when urgent unblinding is considered necessary, a 24-h telephone service will be available. The caller will be told whether the patient received dexamethasone or placebo.

Data collection and management

This trial will be coordinated from Son Espases Hospital. Data will be collected at each site by local investigators and sent to the TSC. These data will be collected from the patient's routine medical records and no special tests will be required.

All data on adverse events, including those routinely collected as outcomes, will be collected and reported as required by the relevant authorities.

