Data will be collected by the investigator on the paper Case Report Forms (CRFs) and transmitted to the TSC through the Research Electronic Data Capture (REDCap). REDCap is a secure web application for building and managing online surveys and databases. Original paper CRFs will remain at each trial site. The data will be used in accordance with local law and ethics committee approval.

Monitoring

The intervention with dexamethasone has marketing authorization in Spain and has been in clinical use for decades. Its safety profile is well established and no significant serious adverse events associated with its use have been identified. The trial will routinely collect data on adverse events which may theoretically be associated with this product and the condition under investigation, and these will be reviewed by the independent DMC.

The trial procedures are based on routine clinical procedures and include (1) the oral administration of the trial drug using routine clinical use; (2) collecting routine clinical information from the medical records; and (3) informed consent. There are no complex procedures or interventions for the participants or investigators in this trial. Clinical management for underlying conditions will remain as per each hospital's standard protocol.

Investigators/institutions are required to provide direct access to source data/documents for trial related monitoring, audits, ethics committee review and regulatory inspection. All trial-related and source documents must be kept for at least 5 years after the end of the trial.

End of trial for participants

For the recruited patients the trial ends at death or at 6-month follow-up, whichever occurs first. If during the treatment phase a patient develops an adverse event, the trial drug should be stopped, the patient treated in line with local procedures, and then followed up.

The trial may be terminated early by the Trial Steering Committee (TSC). The independent DMC may give advice/recommendation for the early termination of the trial but the TSC is responsible for the final decision.

Analysis

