This procedure will be performed again centrally in the 12 de Octubre hospital, Madrid. Previously, the patient's data will be anonymized and the images will be sent through a web platform with a secure server for review. In a central way, the total volume of the contusion will be established as well as the volume of the edema by means of a semi-automatic method using the Analyze software (vesion 10.0; Analyze Direct, Stilwell, Kansas, USA) of which a license is available. The method consists of a semi-automatic analysis in which in each axial section a central voxel is selected and thanks to the density selection, voxels with similar density characteristics are selected.

The performance of measurements in each hospital and subsequent centralization of the images will allow to establish the interobserver and intermethod reproducibility of the measurement of the edema associated with the contusions, in addition to estimating in two ways the difference of measurements at two time points throughout the study and after an intervention.

-Compare the presence of adverse events between the two groups during the 12 days of treatment.

Those adverse effects that have special interest and serious adverse effects will be collected. Side effects of special interest are:

-Metabolic: Hyperglycemia will be especially monitored. The maximum value of capillary glycemia will be recorded daily. The amount of daily insulin that the patient needs to control de glucose level will also be collected.

-Psychiatric: presence of psychotic symptoms using the Confusion Assessment Method (CAM).

-Digestive: Episodes of gastro intestinal hemorrhage; Episodes of epigastric pain, vomiting or reflux symptoms.

-Infectious: Presence of new infectious episodes. Infectious episode will be confirmed in accordance with the Centers for Disease Control (CDC) criteria and mainly based on microbiological criteria.

- Compare the results of the neuropsychological tests between the two groups of patients one month and 6 months after the TBI.

Two neuropsychological evaluations will be performed: 1 month and 6 months after the TBI. Both evaluations will be performed by clinical neuropsychologists, and the protocol to be used will always follow the same procedure and tests. The tests that integrate this protocol are described below:

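### The stopping rule ends trial treatment for any adverse event, with no threshold, and under the planned primary analysis each such stop also removes the patient

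*Combined protocol and SAP*

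**What the plan says.** The only instruction on stopping the drug after an event is in End of trial for participants: "If during the treatment phase a patient develops an adverse event, the trial drug should be stopped, the patient treated in line with local procedures". The patient is then followed up.

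The Definitions section sets the scope of the trigger: "Adverse events (AE): Any undesirable and unintended medical occurrence affecting a trial participant during the course of a clinical trial". Serious adverse events are defined separately, directly below, but the stopping sentence does not use that category.

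Two limits appear under Reporting of adverse events for this trial. The reporting form is restricted to events reasonably attributable to the drug, and "Events that are part of the natural history of the primary event of TBI or expected complications of TBI should not be reported". Both limits govern what is reported. The Monitoring section describes collection more widely, as covering "adverse events which may theoretically be associated with this product and the condition under investigation".

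Supplemental data 1 lists the effects of special interest: hyperglycemia, psychotic symptoms, gastrointestinal bleeding, new infections and "Episodes of epigastric pain, vomiting or reflux symptoms". For glucose it adds: "The amount of daily insulin that the patient needs to control de glucose level will also be collected".

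The Analysis section bases the primary comparison on a modified intention-to-treat set. It leaves out patients with protocol violations, and it defines these as patients who did not complete the 12 days of treatment. Outcome measures states that "the outcome will be collected even if the trial treatment is interrupted or is not actually given".

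**The concern.** A stopping rule should separate events that make continued dosing unsafe from events that can be treated while dosing goes on. This one does not. A raised glucose brought down with insulin, or an episode of reflux, meets the definition of an adverse event and so calls for the drug to be stopped.

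Two things are at stake. First, patients lose part of a short course for reasons that do not require it. Second, a patient stopped in obedience to the protocol becomes a protocol violation and drops out of the primary analysis. The evaluable sample shrinks, and membership of the analysis set depends on something that happened after randomisation and may differ between arms.

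**Working it through.** **1. Does any other text supply a threshold?** The attributability limit and the exclusion of expected TBI complications are worded for the reporting form. If they were carried over to stopping, hyperglycemia, vomiting and reflux would still trigger a stop, because they are listed as effects of special interest, and there would still be no seriousness threshold. Recording daily insulin suggests dosing was meant to continue through treated hyperglycemia. So does Supplemental data 1, which resets the reference neurological score after a sustained worsening. Neither passage says that dosing continues, and no other text allows it to be continued or resumed after an event.

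**2. The plan's sample size.** Inputs from the sample size section: 50% versus 62%, two-sided 5%, about 80% power, 10% inflation, 600 in total. Allocation is 1:1 (Randomization). With pooled variance under the null and average rate 0.56:

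n per arm = [1.96·√(2·0.56·0.44) + 0.8416·√(0.50·0.50 + 0.62·0.38)]² / 0.12² = 267.4, so 268.

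Total 536, and 536/0.9 = 596. The stated 600 reproduces.

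**3. Power when stopped patients are excluded, as the Analysis section provides.**

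Power = Φ[(0.12 − 1.96·SE₀)/SE₁], where SE₀ uses the pooled rate and SE₁ the two separate rates.

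- No exclusions (300 per arm): 84.3%.
- 10% of both arms (270 per arm): SE₀ = 0.04272, SE₁ = 0.04241, (0.12 − 0.08373)/0.04241 = 0.855, power 80.4%.
- 20% of dexamethasone only (300 and 240): SE₀ = 0.04305, SE₁ = 0.04260, (0.12 − 0.08439)/0.04260 = 0.836, power 79.8%.

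| Share excluded (assumed) | Both arms | Dexamethasone only |
|---|---|---|
| 10% | 80.4% | 82.3% |
| 20% | 75.6% | 79.8% |
| 30% | 69.9% | 76.7% |

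These figures keep the true rates at 50% and 62% in the patients who remain. They count lost patients only and say nothing about selection.

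**4. Power when all 600 are analysed.** This is not the planned primary analysis. Here stopped patients stay in and dilute the effect. With s the share of dexamethasone patients stopped and k the share of benefit they keep:

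dexamethasone rate = 0.50 + 0.12·[1 − s(1 − k)].

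From Dose selection, the daily doses are 16, 12, 8, 6, 3 and 2 mg for two days each, in total 2·(16 + 12 + 8 + 6 + 3 + 2) = 94 mg. Assume s = 20% and k equal to the share of dose already taken:

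| Stop after day | Cumulative dose | k | Dexamethasone rate | Power |
|---|---|---|---|---|
| 2 | 32 mg | 34.0% | 60.4% | 72.9% |
| 4 | 56 mg | 59.6% | 61.0% | 77.7% |
| 6 | 72 mg | 76.6% | 61.4% | 80.7% |
| 8 | 84 mg | 89.4% | 61.7% | 82.7% |

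The first row is 0.50 + 0.12·(1 − 0.20·0.660) = 0.604.

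**The case against.** The best defence is that the sentence is loose and the intent narrower. It says should rather than must, the reporting section directs attention to whether complications are relevant to dexamethasone, and insulin use is recorded. It is also a cautious choice for a steroid in TBI, where guidelines advise against high-dose methylprednisolone. Intent probably was narrower, and stopping for ordinary complications of TBI is unlikely in practice. But sites work from the written instruction, and even the narrower reading catches manageable drug effects.

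The sample size also holds a reserve. The 10% inflation is meant for non-adherence, including change of treatment, so the plan promises about 80% power and not 84%. That stands, with the limit that the same 10% must cover withdrawal and loss to follow-up.

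Three stronger readings are tempting, and the documents do not support them:

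- **Power falls to 76%, 66% or 54% with 10%, 20% or 30% stopped.** The dilution formula gives these figures with k = 0, but only if all 600 are analysed and a stopped patient keeps no benefit at all. The planned primary analysis excludes such patients, and 34% of the dose has been given by the end of day 2.
- **Differences between hospitals in applying the rule distort the comparison.** Clinicians are blinded and each hospital has its own list in blocks of two, so differing habits fall on nearly equal arms. The 56-hospital network joins only if the trial continues after the interim analysis.
- **The rule biases the result in a known direction.** Steroid effects could stop more dexamethasone patients, but the literal rule also stops placebo patients, and no rates are given. The exclusion of non-completers is a separate defect of the analysis set. Because outcomes are collected regardless of treatment received, an analysis of everyone randomised remains possible.

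**Conclusion.** The concern holds as a fault in a stated rule: it is broader than the rest of the plan implies, and nothing elsewhere narrows it. Its size is unknown because the documents give no adverse event or stop rate. Under the planned analysis, exclusions of up to about 10% of both arms, from all causes together, leave power near the 80% promised. At 20% to 30% it is about 76% to 70% if both arms are affected equally, and about 80% to 77% if only dexamethasone is. In an analysis of all randomised patients with 20% of the dexamethasone arm stopped, power is about 73% to 83% for stops after day 2 to day 8, if benefit follows dose; that is an assumption. Selection bias is additional, and its direction and size cannot be stated. This is a cheap improvement. The reading of the text is secure; confidence in the practical impact is moderate.

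**What to change.** Replace the stopping sentence in End of trial for participants with:

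> The trial drug is stopped for an adverse event, serious or not, that the responsible clinician judges possibly related to the trial drug and to require discontinuation, or whenever the clinician considers continuation unsafe. Other events, including hyperglycemia controlled with insulin and expected complications of TBI, are managed by local procedures while dosing continues. The day and reason of each stop are recorded, and the patient is followed up.

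The clinician remains free to stop for safety; only the automatic stop goes. The change recovers only the part of the loss that comes from avoidable stops, and it does not repair the exclusion of non-completers from the primary analysis.

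Cost: a protocol amendment needing Trial Steering Committee agreement and regulatory and ethics review, with no extra patients or visits. The case report form is not among the documents; if it does not already hold the day and reason of a stop, two fields are added. Some patients with non-serious events will stay on the drug longer, and some variation between clinicians will remain.

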The primary analysis will compare all patients allocated to dexamethasone versus those allocated to placebo, on an 'modified intention-to-treat' basis. Modified intention-to-treat basis, which will include all patients who were randomly assigned, except those who withdrew consent, those who were lost the follow up or had protocol violations. Protocol violations corresponded to those patients who did not complete the 12-day treatment duration. A descriptive analysis of the baseline variables will be made for each treatment group, followed by a comparison between both groups.

In the secondary analysis a logistic regression model will be built to estimate the effect of dexamethasone and placebo on the patient's functional status measured with the GOSE at one month and at 6 months. The scale will be dichotomized in unfavorable outcome (GOSE 1-6) and favorable outcome (GOSE 7-8). In this analysis the primary outcome will be adjusted by age, pupil reactivity, blood pressure and GCS. To choose a model, the adequacy and goodness of fit will be measured.

Since the severity of the initial injury will significantly determine the final outcome of the patient, regardless of any treatment, the results of this study will be analyzed using the 'sliding dichotomy'. According to this analysis, patients with a less severe initial injury should have a better recovery than those with a severe initial injury. For example, a moderate disability in a patient for whom no more than death or severe disability could be expected is considered a good outcome, and vice versa, consider a moderate disability in a patient with excellent initial prognosis as poor outcome. Patients with a

severe initial injury (GCS score of 4 to 5 or, or with a GCS motor score of 2 to 3) will be considered to have a favorable outcome if the 6-month GOS-E score is 3 or higher. Patients with a moderate-to-severe initial injury (GCS score of 6 to 8 or, GCS motor score of 4 to 5) will be considered to have a favorable outcome if the 6-month GOS-E score is 5 or higher, and those with a less initial injury (GCS score of 9 to 12, GCS motor score of 6) will be considered to have a favorable outcome if the 6-month GOS-E score is 7 or higher.

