The purpose of the sliding dichotomy approach is to increase the sensitivity (to lower the false negative rate) of the analysis. All these variables will also be analyzed in a pre-specified subgroup analysis comparing patients with a pericontusional edema volume of more than 10 mL in the pre-inclusion computed tomography (CT) scan in the study with those who have less than 10 mL of edema volume in the same CT study.

Interim analysis

Since the data available in this type of patients receiving this treatment are scarce and inconclusive as to the primary outcome variable, we will perform an interim analysis. A statistician ([name]) will blindly perform an interim analysis calculating the conditional power, an approach that quantifies the probability of obtaining a significant result at the end of the study given the data available after one year enrolling patients.

Since the probability chosen for futility in this trial is very small (< 0,15), it can be concluded that it would be useless to continue the trial. This interim analysis will be performed at the end of the first year since the inception of the trial, when it is estimated that about 100 patients will have been recruited. At the same time, a safety analysis will be also performed, focused on the adverse effects collected during the first year.

The results will be assessed and discussed by an independent Data Monitoring Committee, formed by one statistician and two experts in TBI, who will inform and make recommendations to the Trial Steering Committee, which will finally make the decisions.

Follow-up

No extra tests are required for the trial but a case report form should be completed at the end of the 12- day treatment, or at death or hospital discharge if either happens sooner. The GOSE and the neuropsychological evaluations will be performed one month and 6 months after the TBI. Both evaluations will be performed by clinical

neuropsychologists, and the protocol used will always follow the same process. The neuropsychological tests that will be performed are described in the Supplemental data

Sponsorship and trial management

This research project has no sponsor. The trial will be coordinated by the Trial Steering Committee (TSC).

Indemnity

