publication of the main trial results will be made. The success of the trial will be dependent entirely upon the collaboration of the nurses and doctors in the participating hospitals and those who hold key responsibility for the trial. Hence, the credit for the study will be assigned to the key collaborator(s) from each participating site, as it is crucial that those taking credit for the work have actually carried it out. The results of the trial will be reported first to trial collaborators.

Financial support

The Sociedad Española de Medicina Intensiva Y Unidades Coronarias (SEMICYUC) is funding the run-in costs for this trial and up to 100 patients' recruitment. Full funding is being sought from public and private funding organizations for the main trial. Funding for this trial covers dexamethasone acquisition, pharmacy expenses and central organizational costs only. The design and management of the study are entirely independent of the manufacturers of dexamethasone or the funders. Review by each Ethics Committee and the Agencia Española del Medicamento (AEMPS) would create a substantial financial burden which could limit the conduct of the trial. We request that payment for review of the protocol by each Committee be waived or set at a reasonable rate to reflect the actual cost of reviewing the trial protocol.

Trial status

Ethics approval obtained from Comité de Ética de la Investigación de las Islas Baleares (CEI-IB) and from Comité de Ética de la investigación del Hospital 12 de Octubre have been obtained. The trial has also been approved by the AEMPS, which is a public agency depending on the Health Ministry of the Spanish government.

Patient recruitment is planned to take place during the first year in Hospital Son Espases (Palma de Mallorca, Spain) and Hospital 12 de Octubre (Madrid, Spain), and is active starting August 2020.

REFERENCES

- 1- Maas AI. Moderate and severe traumatic brain injury in adults. *Lancet Neurol* 2008;7:728.
- 2- Majdan M. Epidemiology of traumatic brain injuries in Europe: a cross-sectional analysis based on hospital discharge statistics and death certificates in 2012. *Lancet Public Health* 2016;1:e76–83.
- 3- Gustavsson A. Cost of disorders of the brain in Europe 2010. *Eur Neuropsychopharmacol* 2011;21:718–79.
- 4- Rosenfeld J. Early management of severe traumatic brain injury. *Lancet* 2012;380:1088-1098.

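### The primary analysis drops every patient who did not complete 12 days of treatment, and no all-randomised analysis is planned

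*Combined protocol and SAP*

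**What the plan says.** All references are to the combined protocol and SAP.

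- **Analysis.** The primary comparison is introduced as covering everyone allocated to each arm. The modified intention-to-treat set is then defined as all randomised patients "except those who withdrew consent, those who were lost the follow up or had protocol violations". Violations are explained in the next sentence: "Protocol violations corresponded to those patients who did not complete the 12-day treatment duration". No reason for non-completion is exempted.
- **End of trial for participants.** "If during the treatment phase a patient develops an adverse event, the trial drug should be stopped"; the patient is then treated locally and followed up.
- **Outcome measures.** "After a patient has been randomized, the outcome will be collected even if the trial treatment is interrupted or is not actually given".
- **Pragmatic design and the uncertainty principle; Eligible patients.** The stated aim is to learn how the treatment performs in routine practice.
- **Other analyses.** No analysis set is named for the adjusted model ("In the secondary analysis a logistic regression model will be built to estimate the effect of dexamethasone and placebo"), the sliding dichotomy, the edema-volume subgroups ("All these variables will also be analyzed in a pre-specified subgroup analysis") or the one-year futility look, at which the statistician "will blindly perform an interim analysis calculating the conditional power".

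No section states an analysis of all randomised patients, whether primary, secondary or sensitivity.

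**The concern.** Despite its label, this is a completers set. The adverse events that the protocol watches for (infection, hyperglycemia, gastrointestinal bleeding, psychotic symptoms) are ones that dexamethasone could influence, and an adverse event leads to stopping. A patient who stops for one of them leaves the primary comparison, although the GOSE is still recorded. Read literally, a patient who dies before day 12 also leaves it, although GOSE 1 belongs to the unfavourable category. The text does not mention deaths in this context.

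Randomisation protects the comparison of everyone randomised. It does not protect a comparison of those who remain after a post-randomisation selection. Bias arises if non-completion is related to outcome and its rate differs between arms, or if the prognosis of the excluded patients differs between arms. Adverse events are compared separately and reviewed by the DMC, but any effect of stopping on recovery can be absent from the headline result. A completers set also does not estimate the real-life effect that the protocol says it wants. If the same set feeds the futility look, it may affect whether the trial expands to the wider hospital network.

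**Working it through.** **The plan's own figure.** Inputs from the sample size section: 50% v 62% good recovery, two-sided 5%, 80% power, 10% inflation. The pooled two-proportion formula gives 268 per arm. Dividing by 0.9 gives 298 per arm, or 596 in total, against the stated 600. The sample size is not in error; the problem is the analysis set.

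**Bias with no true effect.** Let *e* be the proportion excluded in an arm and *g* the good-recovery rate among the excluded. With 50% good recovery overall in both arms, the rate among those analysed is (0.5 − *e·g*)/(1 − *e*). The spurious difference is therefore

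*e*_d(0.5 − *g*_d)/(1 − *e*_d) − *e*_p(0.5 − *g*_p)/(1 − *e*_p),

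where d is dexamethasone and p is placebo. It is zero when *g* = 0.5 in both arms, or when *e* and *g* are the same in both arms.

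Worked case: 10% v 5% excluded, *g* = 20%.
- Dexamethasone: (0.5 − 0.02)/0.90 = 53.3%.
- Placebo: (0.5 − 0.01)/0.95 = 51.6%.
- Difference: +1.75 points. With 270 and 285 patients the standard error is 4.24 points, so the shift is 0.41 standard errors.
- Two-sided rejection probability: Φ(0.41 − 1.96) + Φ(−0.41 − 1.96) = 7.0%.

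All rates below are assumptions, since the documents give none. Randomised: 300 per arm. Type I error comes from 1,000,000 simulated trials per row; the normal approximation agrees within 0.1 point.

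| Excluded, dex v placebo | Good recovery among excluded | Spurious difference (points) | Type I error |
|---|---|---|---|
| 10% v 5% | 50% | 0.0 | 5.0% |
| 10% v 5% | 35% | +0.9 | 5.5% |
| 10% v 5% | 20% | +1.8 | 7.0% |
| 10% v 5% | 0% | +2.9 | 10.6% |
| 8% v 5% | 20% | +1.0 | 5.7% |
| 15% v 5% | 35% | +1.9 | 7.2% |
| 15% v 5% | 20% | +3.7 | 13.9% |
| 15% v 5% (extreme) | 0% | +6.2 | 30.4% |
| 10% v 10% | 20% in both | 0.0 | 5.0% |
| 10% v 10% | 20% v 35% | +1.7 | 6.8% |
| 5% v 10% | 20% | −1.8 | 7.0% |
| 5% v 10% | 0% | −2.9 | 10.7% |

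Equal exclusion rates are therefore not sufficient, and the sign can go either way. These figures concern discarding observed outcomes, not missing ones.

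**Futility look.** The limit is conditional power below 0.15, but the effect assumed for future patients is not stated. With information fraction *t* and drift θ,

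CP = 1 − Φ((1.96 − *z*√*t* − θ(1 − *t*))/√(1 − *t*)).

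At 100 of 600 patients, *t* = 1/6 and the standard error is √(0.5/50) = 0.10.
- Current trend (θ = *z*/√*t*): the limit falls at an observed difference of about 4.1 points (4.0 at 60 patients). An observed 3.0 points gives CP 0.09 and 4.8 points gives 0.195, so a 1.8-point shift can reverse the result.
- Design effect (12 points): CP at zero observed difference is 0.70 to 0.72, depending on the variance convention, and such a shift would not matter.

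**The case against.** The strongest reply is that the harm is possible but not shown. The stopping rule applies to both arms, patients and staff are blinded, and the protocol regards the drug's safety as well established. Every exclusion and recovery rate above is assumed. In the milder scenarios (8% or 10% v 5%, with 20% to 35% recovering well) the bias is 0.9 to 1.8 points against a 12-point target. Type I error above 10% needs nobody among the excluded to recover well, or a threefold difference in exclusion. This is a fair limit on any claim about size. It does not rescue the definition: blinding does not stop drug-related events from differing between arms, and the 10% inflation addresses power, not selection.

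Several narrower points stand:
- The data collected would show unequal exclusions. What is missing is a prespecified analysis that uses the excluded patients' outcomes.
- The removal of early deaths is a literal reading of a text that does not name them, so it is an ambiguity to settle.
- The interim example was chosen to straddle the limit. With a standard error of 10 points, a 1.8-point shift would cross it in about 7% of trials with no effect and about 5% with a 12-point effect, under the current trend. The TSC also makes the final decision.
- The unnamed sets for the secondary analyses are missing detail. One could read the primary definition as applying throughout.

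**Conclusion.** The concern holds. As written, the primary set is conditioned on completing treatment, which treatment can affect, and nothing planned analyses all randomised patients. This conclusion rests on the text alone and needs no assumed rate. Bias is a risk, not a certainty, and its direction is unknown. Under the assumed scenarios with 20% of the excluded recovering well and 3 to 10 points more exclusions on dexamethasone, the spurious difference is 1.0 to 3.7 points and type I error 5.7% to 13.9%. Because it affects the headline result and contradicts the trial's own pragmatic aim and outcome-collection rule, it must be corrected.

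**What to change.** Amend the Analysis section as follows:

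1. Primary set: all randomised patients in their allocated arm, whatever treatment was taken, excluding only those who withdraw consent to use of their data.
2. State that death counts as unfavourable (GOSE 1).
3. Treat loss to follow-up as a missing-outcome problem, with a stated method (multiple imputation is one option) and a sensitivity analysis.
4. Keep 12-day completers as a labelled per-protocol sensitivity analysis.
5. Name the set for the logistic model, sliding dichotomy and subgroups, and use the all-randomised set at the interim.
6. Restate power, saying whether 12 points is the effect in all randomised patients or in completers.

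**Cost.** The amendment needs TSC agreement, ideally before the one-year look. The Trial status section says recruitment "is active starting August 2020", so the amendment should state whether any comparison by arm preceded it. If the interim has been run, it should say which set was used. No new data collection and no change to the treatment-stopping rule are implied.

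The price is possible dilution. If 12 points is already the all-randomised effect, power is 84.3% with 600 outcomes and 80.4% with 540. If it is the effect in completers and a share of the dexamethasone arm stops with no benefit (assumption), the pooled formula gives:

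| Stopping | Effect (points) | Power, 600 outcomes | Power, 540 outcomes |
|---|---|---|---|
| 5% | 12 × 0.95 = 11.4 | 80.4% | 76.2% |
| 10% | 12 × 0.90 = 10.8 | 76.0% | 71.5% |
| 15% | 12 × 0.85 = 10.2 | 71.0% | 66.5% |

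At 10.8 points, 80% power needs 664 outcomes, or 664/0.9 ≈ 738 randomised with 10% missing. The existing 10% inflation pools withdrawal and loss with treatment changes, so it does not show how much dilution was allowed for.
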